4.6 Other Safety Considerations

4.6.1 Adverse Events

Among patients undergoing hemodialysis, adverse events of moderate or higher severity are extremely common and usually result in hospitalizations. Since hospitalization is part of the primary outcome of HiLo, additional information on adverse events will not be collected.

4.6.2 Clinical Safety Laboratory Events

Laboratory measurements are collected either monthly or quarterly for all patients as part of routine clinical care. Predetermined laboratory safety events will be collected. Below are defined the laboratory events of interest in HiLo:

- Hypophosphatemia, defined as serum phosphate <2.0 mg/dL
- Hyperphosphatemia, defined as serum phosphate >7.5 mg/dL
- Hypercalcemia, defined as total uncorrected serum calcium >10.5 mg/dL
- Excessive iron supplementation, defined as serum ferritin >1000 ng/mL and transferrin saturation (TSAT) >50%
- Secondary hyperparathyroidism, defined as parathyroid hormone (PTH) levels greater than 9 times the upper limit of normal for the assay

A listing of laboratory safety events will be created, along with a table of counts of each type of event by treatment group.

4.7 Interim Analysis

An interim analysis is planned for this trial when 50% of planned patients have enrolled with at least 24 months of median follow-up time accrued.

The interim analysis will investigate for futility at two possible levels: futility of enrollment, futility of serum phosphate separation (inability to sustain a separation of ≥ 0.75 mg/dl between arms).

A detailed interim analysis plan will be provided in a separate document.

5. CONVENTIONS

5.1 **Baseline Measurements**

Unless specified otherwise, a baseline value is the last assessment taken prior to the first dialysis session after consent. When there is a missing baseline assessment, it will not be imputed, thus, patients will be excluded from any changes from baseline analysis for which they have a missing baseline value.

5.2 Missing Dates

If a date is missing just the date portion (i.e. year and month are reported) then the date will be imputed with "15". If both the month and date portion are missing, then the date will be

imputed with "June 15". If the imputed date with this method falls before the date of consent, then the date will be imputed with the consent date instead. Likewise, if the imputed date falls after the end of study date, then the date will be imputed with the end of study date.

If additional information is available that allows for a date that is missing both month and day to be deduced as occurring between two other dates, then the date will be imputed as the midpoint between the two known dates that the missing date occurs between. An example of this situation would be if a dialysis date is missing, but is known to have occurred between two other dialysis dates.

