## 4.3.2 Participant Eligibility

The eligibility criteria are broad in order to maximize the generalizability of the trial findings.

- Inclusion criterion:
  - Adults ≥18 years
  - Undergoing 3 times weekly in-center hemodialysis and having received dialysis treatment for at least 3 months
  - Able to provide informed consent
- Exclusion criteria:
  - Females who are pregnant or who plan to become pregnant while in the study
  - Calciphylaxis
  - o Nocturnal in-center dialysis

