2.1.3 In Range 2 (IR2) Population

The IR2 population will be defined similarly to the IR population, except it will include patients that are in range for 50% of their monthly phosphate measures.

2.2 **Protocol Deviations**

Because this is a pragmatic trial intended to evaluate effectiveness of the phosphate targets under real-world conditions, protocol deviations will be limited to: 1) enrollment of individuals who do not meet eligibility criteria or provide informed consent, and 2) breaches of participant confidentiality. Deviations will be reported by the DCRI to the IRB.

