5.3 Other Missing Data

No imputation will be made for missing data other than the date imputation as described section 5.2.

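### SAP 5.2 moves incomplete dates up to the consent date without limiting this to post-consent events, and its bracketing rule leaves out dates missing only the day

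*SAP*

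**What the plan says.** SAP 5.2 imputes the 15th when only the day is missing, and 15 June of the reported year when month and day are both missing. It then sets a floor: "If the imputed date with this method falls before the date of consent, then the date will be imputed with the consent date instead". A matching ceiling applies at the end of study. A further paragraph offers an alternative. It begins "If additional information is available that allows for a date that is missing both month and day to be deduced as occurring between two other" known dates, and concludes "then the date will be imputed as the midpoint between the two known dates that the missing date occurs between". SAP 5.3 adds: "No imputation will be made for missing data other than the date imputation as described section 5.2".

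Other sections bear on how these rules act:

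- Protocol 4.3.2 requires patients "having received dialysis treatment for at least 3 months".
- Protocol 5.4 lists dialysis vintage among the data at study entry. It lists hospitalizations and medications with no stated start of the window, and body weights from every dialysis session.
- SAP 4.3.2 summarises vintage and binder use at baseline.
- SAP 3.1 sets time zero at the first dialysis session after consent, but only for the death component.
- SAP 3.2 counts hospitalizations over the follow-up period without saying when that period begins. SAP 4.5.1 says through what time two patients are compared on hospitalizations, but not from what time.

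**The concern.** A floor at consent is sensible for an event known to have happened on study. SAP 5.2 does not restrict it to such events. The trial draws on existing provider records, and some of the dates in them must precede consent. By the three-month criterion, every eligible patient's dialysis start does. For these dates the rule replaces an approximately right value with one that the record itself contradicts. A binder start recorded only as 2019, for example, would appear to fall on the day of consent.

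The second fault is in the bracketing rule, which is available only when month and day are both missing. A date with a known month is therefore sent to the 15th even when other records show that the 15th is impossible. For deaths this touches the first tier of the primary comparison.

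At stake are the accuracy of baseline descriptions, the placing of admissions close to consent, and the ordering of some deaths.

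**Working it through.** No stated sample size, power or alpha depends on this rule, so there is no figure of the plan to reproduce. The check applies SAP 5.2 as written.

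**Worked cases, consent on 10 March 2022**

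- Dialysis start May 2018: imputed 15 May 2018, before consent, so reset to 10 March 2022. Vintage derived from it is 0 days. A start recorded only as 2018 gives the same result.
- Admission November 2021: imputed 15 November 2021, reset to 10 March 2022, although the recorded month shows that it came earlier.
- Admission recorded only as 2022, true month February: imputed 15 June 2022. This one passes consent through the 15 June step, not through the floor.

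**How often the floor acts, given an incomplete and unbracketed date**

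The rule was applied to 200,000 simulated records. Assumptions: consent spread evenly over 2 years, dialysis start 92 days to 10 years before consent, admissions within the year before consent.

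- Dialysis start, month and year known: 100% get vintage 0. Year only: 99.8% get 0 and 0.2% a negative value.
- Earlier admission, month and year known: 99.2% land on the consent date and 0.8% after it. Year only: 89.8% and 10.2%.

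**Size for vintage, only if it is derived from a start date**

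Shift in mean vintage = share with a partial start date × mean vintage. With an assumed mean of 4 years and assumed shares of 2%, 5% and 10%, the reported mean falls by 0.08, 0.2 and 0.4 years.

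**Size for hospitalizations, only if earlier admissions are transferred and counted from consent**

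Inputs from SAP 1.3: 65% susceptible (100% − 35%), with 2 (Lo) and 1.89 (Hi) admissions per susceptible patient-year. Let f be years of follow-up and q the assumed share of one prior year's admissions moved on study, equal in both arms.

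Ratio = (0.65 × 1.89 × f + q × 0.65 × 2) / (0.65 × 2 × f + q × 0.65 × 2)

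| q | f = 2 | f = 3 |
|---|---|---|
| 0 | 0.945 | 0.945 |
| 1% | 0.9453 | 0.9452 |
| 5% | 0.9463 | 0.9459 |
| 10% | 0.9476 | 0.9468 |

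For f = 2 and q = 10%: (2.457 + 0.13) / (2.6 + 0.13) = 2.587 / 2.73 = 0.9476. This is a ratio of mean counts, not the Finkelstein-Schoenfeld statistic, and it ignores deaths and dropout.

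Protocol 8.1 assumes 1.8 and 1.53 admissions instead. The same case then gives (1.989 + 0.117) / (2.34 + 0.117) = 2.106 / 2.457 = 0.857, against 0.85 with no misplacement. The dilution is again small.

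**Deaths missing only the day**

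A patient has a recorded session on 28 March and a death recorded as March. The true date lies between 28 and 31 March. SAP 5.2 gives 15 March, which is 13 days before a treatment the database holds. In general, a death on the 31st is dated 31 − 15 = 16 days early, and a death on the 1st is dated 15 − 1 = 14 days late.

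**The case against.** The strongest reply is that the trigger may seldom occur and that the consequences do not follow automatically. Most of this stands.

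- **Vintage.** Protocol 5.4 lists vintage itself and no dialysis-start date, and Protocol 10.3 allows dates to be supplied as elapsed times. If vintage arrives as a duration, SAP 5.2 never touches it. Vintage appears only in the baseline table and is not among the adjustment variables in SAP 4.5.3.
- **Eligibility.** A reader might infer that affected patients would be recorded as deviations, since SAP 2.2 includes "enrollment of individuals who do not meet eligibility criteria or provide informed consent". The documents do not support this. Protocol 5.2 establishes eligibility from provider systems at identification, and no section derives deviations from imputed dates.
- **Hospitalizations.** A reader might infer that earlier admissions simply become on-study events. If counting starts at the SAP 3.1 time zero, an admission placed on the consent date falls before it and is not counted, unless consent and that session share a day. It is also not settled that earlier admissions are transferred.
- **Data quality.** Protocol 1.2 describes hospitalization and death capture as precise and in real time. Under Protocol 10.1 each cumulative transfer overwrites the last, so a completed date can later replace a partial one. SAP 5.3 bars other imputation, not data correction.
- **Scope.** Not every incomplete date is affected, because the bracketing rule covers some dates missing both month and day.

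These points limit the harm but do not repair the text. Bracketing never helps a date with a known month, and an unbracketed historical date remains exposed. None of these points answers the death example.

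**Conclusion.** The concern holds as a fault in a stated rule. Followed literally, SAP 5.2 overwrites dates that the record shows to precede consent, and it can date a death before a recorded dialysis session although session-level data are held. Zero vintage in the baseline table and extra on-study admissions are conditional consequences that depend on derivations the documents do not state.

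The effect on the primary result is probably small. The frequency of partial dates is not given, and the shares above are assumptions. Among individually randomized participants the error should be similar in both arms. The illustrated ratio moves from 0.945 to at most 0.9476, towards no difference. A death misdated by up to 16 days early or 14 days late changes a pairwise result only where it alters an ordering. A reader might infer that the trial's conclusion is at risk, but nothing in the documents shows that. The correction is still worth making in advance, because in an open-label trial the alternative is an unplanned programming decision.

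**What to change.** Amend SAP 5.2 and SAP 3.1–3.2 as follows.

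1. Limit the consent-date floor to events known to follow consent. Leave unfloored any date whose reported month or year precedes consent, or that by definition precedes consent (such as dialysis start), and cap it at the day before consent.
2. Apply the known-neighbouring-dates rule also when only the day is missing, so that no death is dated before the last recorded session. A death has no later session, so the end of the reported month can serve as the upper bound. In the example, the midpoint of 28 and 31 March is 29 or 30 March.
3. State that hospitalization counting starts at the same time zero as death. For admissions partially dated within the consent month or year, use session records and admission and discharge dates to place them. Exclude those known to have begun before time zero. Apply the floor only where timing remains undetermined, and say whether such an admission is counted.

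Two simpler rules should be avoided. Counting only admissions whose known month or year is later than that of consent would drop genuine on-study admissions in the consent month or year. Accepting any post-consent discharge would count stays that began before consent.

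The cost is a few sentences and minor extra programming, with no new data.

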5.3 Other Missing Data

No imputation will be made for missing data other than the date imputation as described section 5.2.

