## 8.5 Other Planned Secondary Analyses

As an alternative approach to analyzing the secondary outcome of hospitalization, the analysis will be repeated after substituting individual participants' total number of days spent in the hospital per total length of follow-up in HiLo. Additional secondary outcomes related to nutrition are change from baseline in serum albumin, and PCR. Mixed effect models will be used for all available longitudinal observations in the ITT population to compare change from baseline in these secondary continuous variables between the two arms. Supplemental analyses will consider the "as treated" sample.

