3.2 Secondary Endpoints

Time to all cause death and PPY hospitalization rates will be investigated separately as secondary endpoints. The patient level PPY hospitalization rate will be calculated by dividing the patient's number of hospitalizations during the follow-up period by the total length of the patient's follow-up time in years.

Other secondary outcomes will be the change from baseline in the following clinical measures: serum albumin and PCR. The baseline measure for these will be the latest available measure before consent.

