4.5.3 Additional Analyses

An adjusted analysis of the main secondary endpoints will be performed. The following adjustment variables will be included in the models:

- Age
- Sex
- Race
- Calculated BMI
- Cause of end-stage renal disease
- Vascular access type

The covariance structure for the model will be selected in the same manner as for the serum albumin and PCR analyses described in section 4.5.2.

An adjusted analysis of time to all-cause death will be performed by repeating the analysis of the endpoint described in section 4.5.2, but including the same adjustment variables listed for the adjusted analysis of the primary endpoint in the Cox model.

Similarly, the analyses for the serum albumin and PCR will be repeated including the same adjustment variables in their respective models.

The ratio of hospitalized days will be tested with the following hypotheses:

 $H_0: \mu_H = \mu_L vs. H_1: \mu_H \neq \mu_L$

Where μ_H and μ_L are the mean ratio of hospitalized days in the Hi and Lo treatment arms respectively. If the two-sided 95% confidence interval for the difference in the mean ratios does not include 0, then the null hypothesis will be rejected.

Under a previous HiLo protocol, cluster randomization at the site level occurred but otherwise participants were enrolled and participated in the study in a similar manner to the current protocol. If it is determined to be appropriate, the primary outcomes of the participants enrolled under the cluster randomization will be analyzed separately. Furthermore, the results of this analysis will be combined with the primary analysis detailed in this SAP using meta-analysis methods. Details of both the analysis of the cluster randomized data and the meta-analysis will be provided in a future version of this document.

Additional analyses concerning COVID-19

Additional analyses are planned to investigate and control for the potential effect of the COVID-19 outbreak on the other planned analyses. If the data are available to construct an endpoint as described in section 3.3, then the primary and secondary analyses will be repeated using only non-COVID-19 related deaths and hospitalizations as endpoint events. Patients experiencing a death attributed to COVID-19 will be censored at the time of death.

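### The SAP's rules on missing baseline data needlessly remove patients from the albumin and PCR analyses and, by default, from the covariate-adjusted models; the primary and main unadjusted analyses are untouched

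*SAP*

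**What the plan says.** SAP 5.3 is general: "No imputation will be made for missing data other than the date imputation". SAP 5.1 applies the same approach to baselines. A missing baseline is not filled in, and "patients will be excluded from any changes from baseline analysis for which they have a missing baseline value". That covers serum albumin and PCR, which SAP 3.2 defines as changes from baseline, with the rule "The baseline measure for these will be the latest available measure before consent" and no look-back limit.

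SAP 4.5.3 adds supportive models: "An adjusted analysis of the main secondary endpoints will be performed". It then says "The following adjustment variables will be included in the models" and lists age, sex, race, BMI, cause of end-stage renal disease and vascular access type. The list also carries over to the nutrition outcomes, since "the analyses for the serum albumin and PCR will be repeated including the same adjustment variables in their respective models", and to the second COVID-19 adjustment model. No rule is given for a patient with a blank covariate.

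On the protocol side, section 8.5 says "Mixed effect models will be used for all available longitudinal observations in the ITT population", and the sentence goes on to make change from baseline the quantity compared. Protocol 8.2 ties the all-randomized ITT sample to the primary efficacy analysis. SAP section 6 declares no departures from the protocol.

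**The concern.** All covariates come from routine provider records. When imputation is barred and no other rule is given, standard model fitting drops any patient with one blank covariate, together with that patient's death or hospitalization data. The adjusted estimate then comes from a smaller and possibly different set of patients than the unadjusted one. A difference between the two could reflect who was lost and not the adjustment.

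For albumin and PCR the exclusion is written out. One absent pre-consent value cancels every follow-up value that the patient supplies. Baseline covariates in a randomized trial can be filled in without using arm or outcome and without biasing the arm comparison, so the exclusion buys nothing.

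**Working it through.** **1. Which analyses the rules reach**

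| Analysis | Needs a covariate or baseline lab? | Patients removed |
|---|---|---|
| Primary Finkelstein-Schoenfeld test (SAP 4.5.1) | No; every patient is scored | 0 |
| Time to death, Cox (SAP 4.5.2) | No; arm only | 0 |
| Hospitalization rate difference (SAP 4.5.2) | No | 0 |
| Albumin and PCR (SAP 4.5.2) | Yes, a baseline value | Explicit exclusion (SAP 5.1) |
| Adjusted main secondary, albumin and PCR models (SAP 4.5.3) | Yes, six covariates | By inference from SAP 5.3 |
| Second COVID-19 adjustment model (SAP 4.5.3) | Yes, the same six plus infection status | By inference from SAP 5.3 |

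**2. The plan's own figure.** Protocol 8.1 states at least 80% power for mortality as a separate endpoint. Inputs are 3,800 patients, 15% annual mortality, hazard ratio 0.85 and 5% annual loss (Protocol 8.1), with 1:1 allocation and uniform censoring at 2–4 years (SAP 1.3).

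- Death hazards are −ln(0.85) = 0.1625 and 0.85 × 0.1625 = 0.1381. The loss hazard is −ln(0.95) = 0.0513.
- Expected deaths are about 678 + 596 = 1,274.
- Power = Φ(√1,274/2 × 0.1625 − 1.96) = Φ(0.94), or about 82.6%.

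The stated figure reproduces. It belongs to the arm-only Cox model, which loses nobody, so it does not move.

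**3. Patients lost from an adjusted model.** The documents give no missingness rate, so m per field is an assumption. If gaps are independent across k fields, loss = 1 − (1 − m)^k. If they all fall in the same patients, loss = m. With N = 3,800:

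| Pattern | m = 1% | m = 2% |
|---|---|---|
| Same patients | 1.0% (38) | 2.0% (76) |
| Three fields, independent | 1 − 0.99³ = 3.0% (113) | 1 − 0.98³ = 5.9% (223) |
| Six fields, independent | 1 − 0.99⁶ = 5.9% (222) | 1 − 0.98⁶ = 11.4% (434) |

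The three-field row is the more plausible independent case. Age is needed for eligibility, weights are recorded every session and access type monthly (Protocol 4.3.2 and 5.4). That leaves mainly race, height and cause of renal disease.

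**4. Patients lost from albumin or PCR.** The loss equals the share with no baseline value: 38 patients at 1%, 76 at 2%. It is probably at the low end. Eligibility requires at least 3 months of dialysis, these labs are drawn monthly, and the latest earlier value counts however old it is.

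**5. Why the exclusion is unnecessary.** SAP 4.5.2 already puts baseline in the mixed model. Write Y for follow-up and B for baseline. The change model Y − B = a + τ·arm + β·B + error rearranges to Y = a + τ·arm + (β + 1)·B + error. The arm effect τ is the same in both. Modelling Y asks the same question, and a patient without B can stay in once the baseline covariate is filled in.

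**The case against.** The strongest reply is that nothing the trial's main conclusions rest on is affected. That stands, as the first table shows.

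Several stronger readings are tempting, and the documents do not support them:

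- **That the rules breach the protocol's ITT commitment.** The all-randomized sentence in Protocol 8.2 concerns the primary efficacy analysis, which keeps every patient. The protocol describes no covariate-adjusted analysis, so it promises nothing about one.
- **That SAP 5.1 flatly contradicts Protocol 8.5.** The protocol sentence goes on to name change from baseline. A patient without a baseline has no observed change, so SAP 5.1 can be read as applying that endpoint. What remains is tension: the protocol speaks of all available observations, and the SAP discards usable ones.
- **That the SAP prescribes deletion for a blank covariate.** It does not. Deletion follows from barring imputation and giving no other rule. A separate category for missing values might be called coding and not imputation, which is a reason to state the rule.
- **That mortality power falls below 80%.** Cutting the 1,274 deaths by 5.9% or 11.4% in the formula above gives about 80% or 78%. However, the stated power is not for the adjusted model, and this sum ignores any gain from adjustment.

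The size is also uncertain. Protocol 1.2 reports that an earlier dialysis trial using a similar approach found most data elements highly complete. A difference between adjusted and unadjusted results could also be checked by refitting the unadjusted model on the same patients, although the SAP does not plan this.

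**Conclusion.** The point holds in limited form. SAP 5.1 expressly removes patients without a baseline from two secondary analyses. SAP 5.3, with no rule for blank covariates, makes the supportive adjusted models complete-case by default. Both losses are avoidable.

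For the adjusted models, the loss is about 1–2% of 3,800 if gaps coincide, 3–6% with independent gaps in three fields, and 6–11% with independent gaps in all six. All of this rests on an assumed 1–2% per field. Equal, independent gaps in all six fields is an upper-end pattern, and larger losses require higher assumed rates that nothing in the documents supports. Loss from albumin and PCR is probably small.

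The primary result, the unadjusted secondary results for mortality and hospitalization, and the stated power are not in question.

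**What to change.** - **SAP 5.1 and 5.3:** allow handling of missing baseline covariates only, without reference to arm or outcome. Use a separate category for missing values of categorical variables, and the overall mean plus a missingness indicator for continuous ones, including baseline albumin and PCR. Outcomes stay unimputed.
- **SAP 3.2 and 4.5.2:** model follow-up albumin and PCR adjusted for baseline, so patients without a baseline remain.
- **SAP 4.5.3:** report the number of patients analysed in each model, including the second COVID-19 adjustment model.
- **SAP section 6:** list the change if it departs from the protocol's wording.

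The cost is a few extra model terms and short edits in several SAP sections. No new data are needed. Settling the rule before results are seen also removes a later discretionary choice.
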